6.3 Preparation/Handling/Storage/Accountability

Guidance and information on preparation, handling, storage, accountability, destruction, or return of the investigational product during the study are provided in the IPIM.

6.4 Measures to Minimize Bias: Randomization and Blinding

6.4.1 Method of Treatment Assignment

Subjects who meet eligibility criteria will be assigned to treatment with AMG 510.

6.4.2 Blinding

This is an open-label study that is not blinded.

6.5 Treatment Compliance

A paper diary will be provided to subjects at the beginning of each cycle and the study staff will provide guidance to the subjects on how to complete the diary.

Compliance with treatment and the corresponding assessments should be followed according to the Schedule of Activities (Section 1.3) and the treatment procedures (Section 8.2).

6.6 Treatment of Overdose

Neither the effects of overdose of AMG 510 nor an antidote to overdose are known.

For this study, any dose of AMG 510 greater than 960 mg QD within an 18-hour time period will be considered an overdose.

In the event of an overdose, the investigator/treating physician should:

- Contact Amgen medical monitor immediately.
- Closely monitor the participant for any adverse event/serious adverse event and laboratory abnormalities for at least 7 days.
- Document the quantity of the excess dose as well as the duration of the overdose in the Case Report Form (CRF).

6.7 Prior and Concomitant Treatment

6.7.1 Prior Treatment

Prior therapies that were being taken/used from the original diagnosis through enrollment will be collected. For prior anticancer therapies, collect line of therapy, regimen/agent, type of therapy, setting, start date, stop date, reason for stopping therapy, dose, unit, route, frequency, best response, date of best response, and date of progression documented. For prior radiotherapy for current malignancy, collect body

site, sub site, setting, type, start date, stop date, total dose, unit, best response, was chemotherapy part of concurrent therapy, did documented progression occur in this area, date progression documented. For prior surgeries for current malignancies collect date of surgery, surgery, reason for surgery, body site, subsite, intent of surgery, residual disease.

All other prior therapies that were being taken 28 days before enrollment through enrollment should be collected on each subject's eCRF(s). Collect therapy name, indication, dose, unit, frequency, route, start date, and stop date.

6.7.2 Concomitant Treatment

Throughout the study, investigators may prescribe any concomitant medications or treatments deemed necessary to provide adequate supportive care except for those listed in Section 6.1.7.

Concomitant administration of AMG 510 with **PPI (eg, Omeprazole) or** H2-receptor antagonists (eg, famotidine) decreased AMG 510 concentrations, which may reduce AMG 510 efficacy. Avoid use of PPI or H2-receptor antagonists with AMG 510. If antacid therapy is considered medically necessary, administer AMG 510 4 hours before or 10 hours after administration of a local antacid.

Breast cancer resistance protein substrates should be used with caution when co-administered with AMG 510 which may increase the circulating concentration of BCRP substrates.

Amgen will review all concomitant medications with the investigators prior to dosing with AMG 510 to ensure patient safety.

All concomitant therapies (including all prescription, over-the-counter medications) are to be collected from enrollment through the end of the SFU period and will be recorded on the eCRF.

For concomitant therapies, collect therapy name, indication, dose, unit, frequency, route, start date and stop date.

7. Discontinuation Criteria

Subjects have the right to withdraw from investigational product and/or other protocol-required therapies, protocol procedures, or the study as a whole at any time and for any reason without prejudice to their future medical care by the physician or at the institution.

The investigator and/or sponsor can decide to withdraw a subject(s) from investigational product, device, and/or other protocol-required therapies, protocol procedures, or the study as a whole at any time prior to study completion for the reasons listed in Sections 7.1, 7.2.1, and 7.2.2.

7.1 Discontinuation of Study Treatment

Subjects (or a legally acceptable representative) can decline to continue receiving investigational product and/or other protocol-required therapies or procedures at any time during the study but continue participation in the study. If this occurs, the investigator is to discuss with the subject the appropriate processes for discontinuation from investigational product or other protocol-required therapies and must discuss with the subject the possibilities for continuation of the Schedule of Activities (see Table 1-1) including different options of follow-up (eg, in person, by phone/mail, through family/friends, in correspondence/communication with other treating physicians, from the review of medical records) and collection of data, including endpoints and adverse events, and must document this decision in the subject's medical records. Subjects who have discontinued investigational product and/or other protocol-required therapies or procedures should not be automatically removed from the study. Whenever safe and feasible, it is imperative that subjects remain on-study to ensure safety surveillance and/or collection of outcome data.

Subjects may be eligible for continued treatment with Amgen investigational product(s) and/or other protocol-required therapies by a separate protocol or as provided for by the local country's regulatory mechanism, based on parameters consistent with Section 11.3.

Reasons for early removal from protocol-required investigational product(s) or procedural assessments may include any of the following:

- decision by Sponsor
- lost to follow-up
- death
- adverse event
- subject request
- protocol deviation
- non-compliance
- requirement for alternative therapy

- disease progression as defined by RECIST version 1.1 criteria (Section 11.8)
- pregnancy

7.2 Discontinuation From the Study

Withdrawal of consent for a study means that the subject does not wish to receive further protocol-required therapies or procedures, and the subject does not wish to or is unable to continue further study participation. Subject data up to withdrawal of consent will be included in the analysis of the study, and where permitted, publicly available data can be included after withdrawal of consent. The investigator is to discuss with the subject appropriate procedures for withdrawal from the study and must document the subject's decision to withdraw in the subject's medical records.

If a subject withdraws from the study, he/she may request destruction of any samples taken and not tested, and the investigator must notify Amgen accordingly (see Section 11.6 for further details). Refer to the Schedule of Activities (Table 1-1) for data to be collected at the time of study discontinuation and follow-up and for any further evaluations that need to be completed.

7.2.1 Reasons for Removal From Washout Period, Run-in Period, or Invasive Procedures

Not applicable to the study.

7.2.2 Reasons for Removal From Study

Reasons for removal of a subject from the study are:

- Decision by sponsor
- Withdrawal of consent from study
- Death
- Lost to follow-up

7.3 Lost to Follow-up

A subject will be considered lost to follow-up if he or she repeatedly fails to return for scheduled visits and is unable to be contacted by the study site.

The following actions must be taken if a subject fails to return to the clinic for a required study visit:

• The site must attempt to contact the subject and reschedule the missed visit as soon as possible and counsel the subject on the importance of maintaining the assigned visit schedule and ascertain whether or not the subject wishes to and/or is able to continue in the study.

- In cases in which the subject is deemed lost to follow-up, the investigator or designee must make every effort to regain contact with the subject (where possible, 3 telephone calls and, if necessary, a certified letter to the subject's last known mailing address or local equivalent methods). These contact attempts are to be documented in the subject's medical record.
- If the subject continues to be unreachable, he/she will be considered to have withdrawn from the study with a primary reason of lost to follow-up.
- For subjects who are lost to follow-up, the investigator can search publicly available records where permitted to ascertain survival status. This ensures that the data set(s) produced as an outcome of the study is/are as comprehensive as possible.

8. Study Assessments and Procedures

Study procedures and their time points are summarized in the Schedule of Activities (see Table 1-1).

As protocol waivers or exemptions are not allowed if an enrolled subject is subsequently determined to be ineligible for the study, this must be discussed with the sponsor immediately upon occurrence or awareness to determine if the subject is to continue or discontinue study treatment.

Adherence to the study design requirements, including those specified in the Schedule of Activities, is essential and required for study conduct.

Ongoing patients who are unable or unwilling to attend protocol-specified trial visits and procedures should generally remain on study even if AMG 510 is interrupted, as continued collection of even limited clinical information is valuable for safety and efficacy assessments. In cases where the patient is unable to visit the site, Amgen has explored alternative methods for safety assessments and continuation of study medication (eg, phone contact, virtual visit, alternative location for assessment including local labs or radiological assessment, direct to patient shipment of investigational product where possible). Each case should be discussed with the medical monitor before temporary adjustments are made to the subject's schedule of activities.

8.1 General Study Periods

8.1.1 Screening, Enrollment and/or Randomization

Informed consent must be obtained before completing any screening procedure or discontinuation of standard therapy for any disallowed therapy. After written consent has been obtained, subjects will be screened in order to assess eligibility for study participation. Laboratory assessments that were performed as standard of care prior to signing the informed consent may be used for screening assessments if

they were performed within the allowed 28-day screening window prior to cycle 1day 1. All screening procedures must be performed within 28 days prior to start of investigational product administration, unless otherwise noted.

Subjects who meet the inclusion and exclusion criteria will be eligible to be enrolled in the study. If a subject has not met all eligibility criteria at the end of the 28-day window, the subject will be registered as a screen failure. Subjects who screen fail may be eligible for re-screening at the investigator's discretion after consultation with Amgen (see also below for details on re-screening).

Laboratory assessments used to determine subject eligibility may be repeated once for confirmation during the 28-day screening period before the subject is considered a screen failure. If laboratory assessments are repeated during the screening period, the result of the last sample taken prior to start of treatment with AMG 510 will be taken into account for determination of subject eligibility.

The following procedures are to be completed during the screening period at the time points designated in the Schedules of Activities (Table 1-1).

Assessments that were performed as standard of care prior to signature of informed consent, but within **the allowed 28**-day **screening window** prior to start of treatment with AMG 510 can be used as screening assessments and do not need to be repeated to confirm subject eligibility.

Rescreening:

Subjects may be rescreened up to 2 times at the discretion of the investigator, after consultation with Amgen. The subject must be reconsented if a rescreening attempt occurs more than 30 days after the original signing of the ICF.

Rescreened subjects must be documented as screen-failed in the subject's medical record and subsequently documented as rescreened. Subjects will retain the same subject identification number assigned at the time of initial screening. Once the subject is recorded as rescreened, a new 28-day screening window will begin. The following assessments do not have to be repeated during rescreening, if they were performed as standard of care or during the initial screening attempt within the time frames specified below:

• Hepatitis serology does not need to be repeated if it was performed within 6 weeks prior to start of treatment with AMG 510.

- Imaging assessments do not need to be repeated if they were performed within 4 weeks prior to start of treatment with AMG 510.
- Central confirmation of KRAS p.G12C status (if applicable)

Any other assessments do not need to be repeated if they were performed within **the allowed 28-day screening window** prior to start of treatment with AMG 510.

8.1.2 Treatment Period

Treatment begins on day 1 of cycle 1 when the first dose of investigational product is administered to a subject. AMG 510 will be administered orally QD for 21-day cycles, with no drug holidays between each cycle.

During clinic visit days all protocol-required predose assessments have to be performed prior to administration of AMG 510. Predose is defined as a time before dosing. For laboratory assessments, predose assessments may be performed within \pm 1 day for cycle 1 (except cycle 1 day 1 and cycle 1 day 8 where the window is -1 day) and cycle 2 and \pm 2 days after cycle 2.

Results of any predose laboratory tests will not have to be available before the administration of AMG 510. Laboratory assessments that were done within 24 hours prior to AMG 510 administration do not need to be repeated.

AMG 510 will be dispensed to subjects at the beginning of each cycle and the subjects are required to bring the bottle of AMG 510 to clinic during clinic visit days. AMG 510 administration should be done in the clinic after all pre-dose assessments have been performed during clinic visit days.

A paper diary will be provided to subjects at the beginning of each cycle and the study staff will provide guidance to the subjects on how to complete the diary.

Administration of AMG 510 may continue until there is evidence of disease progression, intolerance to study medication, or withdrawal of consent.

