- ^f A single ECG must be performed at screening to fulfill inclusion criteria. In addition, 3 triplicate ECGs must be performed prior to the first dose of AMG 510 to serve as baseline. For all other visits, 1 triplicate ECG must be performed (See Section 8.2.3.2).
- ⁹ Assessments to be performed on day 1 of every other cycle starting in cycle 3 (eg, C3, C5, C7, etc). Laboratory assessments may be performed within 24 hours before day 1 of cycle 1. Lipid panel may include total cholesterol, HDL, and LDL depending on local standard practice for cholesterol testing, and triglycerides.
- ^h Microscopic exam to be performed at the discretion of the investigator.
- ¹ For female subjects of childbearing potential only. At screening, a highly sensitive serum pregnancy test is required. For all other time points, a highly sensitive serum or urine pregnancy test is required.
- ¹ If KRAS p.G12C status is not available in the subject's medical record, archived FFPE tissue (collected within 5 years) may be used for KRAS p.G12C screening by local or central testing (as applicable). If archived FFPE tissue is unavailable, a tumor biopsy may be performed.
- ^k Radiological imaging and tumor assessments are required at screening and every 6 ± 1 weeks for the first 4 response assessments. After four 6-week response assessments, radiological imaging and tumor assessments will be performed every 12 ± 1 weeks. Imaging and tumor assessments will continue until disease progression, start of new anticancer treatment, death, withdrawal of consent, or until end of study. MRI/CT scans can be obtained earlier if clinical deterioration necessitates an earlier scan at the discretion of the managing physician. End of treatment CT/MRI should be performed only for subjects that discontinue treatment for a reason other than disease progression per RECIST 1.1 criteria. Every assessment must include the chest, abdomen, pelvis, and all other known sites of disease. Tumor burden assessments will be performed based on RECIST 1.1 guidelines (Section 11.8). Radiographic response (CR and PR) requires confirmation by a repeat assessment at least 4 weeks after the first detection of response.

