- 208 Unresolved toxicities from prior anti-tumor therapy, defined as not having resolved to Common Terminology Criteria for Adverse Events (CTCAE) version 5.0 grade 0 or 1, or to levels dictated in the eligibility criteria with the exception of alopecia (grade 2 or 3 toxicities from prior anti-tumor therapy that are considered irreversible [defined as having been present and stable for > 6 months], such as ifosfamide related proteinuria, may be allowed if they are not otherwise described in the exclusion criteria and there is agreement to allow by both the investigator and sponsor)
- 209 Anti-tumor therapy (chemotherapy, antibody therapy, molecular targeted therapy, retinoid therapy, hormonal therapy [except for subjects with breast cancer], or investigational agent) within 28 days of study day 1; concurrent use of hormone deprivation therapy for hormone-refractory prostate cancer or breast cancer is permitted
- 210 Therapeutic or palliative radiation therapy within 2 weeks of study day 1. Subjects must have recovered from all radiotherapy-related toxicity.
- 211 Currently enrolled in another investigational device or drug study, or less than 28 days since ending another investigational device or drug study(s), or receiving other investigational agent(s)
- 212 Other investigational procedures are excluded

- 213 Major surgery within 28 days of study day 1
- 214 Female subjects of childbearing potential who are unwilling to use 1 highly effective method of contraception during treatment of AMG 510 and for an additional 7 days after receiving the last dose of AMG 510. Refer to Section 11.5 for additional contraceptive information.
- 215 Female subjects who are lactating/breast feeding or who plan to breastfeed while on study and for an additional 7 days after receiving the last dose of study drug
- 216 Female subjects with a positive pregnancy test assessed at screening by a highly sensitive serum pregnancy test
- 217 Female subjects planning to become pregnant while on study and for an additional 7 days after receiving the last dose of AMG 510
- 218 Male subjects with a female partner of childbearing potential who are unwilling to practice sexual abstinence (refrain from heterosexual intercourse) or use contraception during treatment and for an additional 7 days after the last dose of AMG 510. Refer to Section 11.5 for additional contraceptive information.

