8.2.5 Clinical Laboratory Assessments

Refer to Section 11.2 for the list of clinical laboratory tests to be performed and to the Schedule of Activities (Table 1-1) for the timing and frequency.

The investigator is responsible for reviewing laboratory test results and recording any clinically relevant changes occurring during the study in the Event eCRF. The investigator must determine whether an abnormal value in an individual study subject represents a clinically significant change from the subject's baseline values. In general, abnormal laboratory findings without clinical significance (based on the investigator's judgment) are not to be recorded as adverse events. However, laboratory value changes that require treatment or adjustment in current therapy are considered adverse events. Where applicable, clinical sequelae (not the laboratory abnormality) are to be recorded as the adverse event.

All protocol-required laboratory assessments, as defined in Section 11.2, must be conducted in accordance with the laboratory manual and the Schedule of Activities (Table 1-1).

Pregnancy Testing

A highly sensitive serum pregnancy test should be completed at screening and a highly sensitive serum or urine pregnancy test should be completed within 7 days of initiation of investigational product and within 7 days of day 1 of each cycle for females of childbearing potential.

Note: Females who have undergone a bilateral tubal ligation/occlusion should have pregnancy testing per protocol requirements. (If a female subject, or the partner of a male subject, becomes pregnant it must be reported on the Pregnancy Notification Form, see Figure 11-2). Refer to Section 11.5 for contraceptive requirements.

Additional serum or urine pregnancy testing should be performed as outlined in the Schedule of Activities (Table 1-1).

Additional on-treatment pregnancy testing may be performed at the investigator's discretion or as required per local laws and regulations.

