11.2 Appendix 2. Clinical Laboratory Tests

The tests detailed in Table 11-1 will be performed by the central laboratory and/or by the local laboratory.

Protocol-specific requirements for inclusion or exclusion of subjects are detailed in Sections 5.1 to 5.2 of the protocol.

Additional tests may be performed at any time during the study as determined necessary by the investigator or required by local regulations.

Local Laboratory: Chemistry	Local Laboratory: Coagulation	Local Laboratory: Urinalysis	Local Laboratory: Hematology	Central Laboratory
sodium potassium chloride bicarbonate total protein albumin calcium magnesium phosphorus glucose BUN or urea creatinine total creatine kinase total bilirubin direct bilirubin direct bilirubin ALP AST (SGOT) ALT (SGPT) Glomerular filtration rate (derived)	PT/INR PTT/aPTT fibrinogen (optional) D-dimer (optional) Local Laboratory: Serology Hep B surface antigen Hep C antibody Anti-HBs Local Laboratory: Thyroid Panel TSH Total T3 (or free T3 per local standard) Free T4 Local Laboratory: Lipid Panel total cholesterol LDL	specific gravity pH blood protein glucose bilirubin ketones sodium (optional) potassium (optional) Microscopic exam ^c : • cellular casts • granular casts • hemoglobin casts • hyaline casts • hyaline casts • mixed casts • WBC • RBC • epithelial cells • bacteria • urine casts	RBC hemoglobin hematocrit MCV platelets calculated absolute neutrophil count (derived) WBC differential: • total neutrophils • bosophils • basophils • lymphocytes • monocytes	PK sampling tumor biopsy ^b

Table 11-1. Analyte Listing

Local Laboratory: Chemistry	Local Laboratory: Coagulation	Local Laboratory: Urinalysis	Local Laboratory: Hematology	Central Laboratory
	HDL			
	triglycerides			
	Local Laboratory: Other			
	HbA1c			
	Serum or urine pregnancy ^a			

Footnotes defined on next page

ALP = alkaline phosphatase; ALT = alanine aminotransferase; aPTT = activated partial thromboplastin time; AST = aspartate aminotransferase; BUN = blood urea nitrogen; HbA1c = hemoglobin A1c; HDL = high density lipoprotein; Hep = hepatitis; HIV = human immunodeficiency virus; INR = international normalized ratio; LDL = low density lipoprotein; MCV = mean corpuscular volume; PK = pharmacokinetics; PT = prothrombin time; PTT = partial thromboplastin time; RBC = red blood cell count; SGOT = serum

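### Section 8.1.2 has no first-dose exception, so in a female of childbearing potential the second pregnancy test may be unread when AMG 510 is first given (low severity, cheap to fix)

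*Protocol*

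**What the plan says.** Protocol Section 8.1.2 (Treatment Period) gives a general rule on predose laboratory work: "Results of any predose laboratory tests will not have to be available before the administration of AMG 510". The same section explains the term: "Predose is defined as a time before dosing". Cycle 1 day 1 is singled out there only for when the sample may be collected (a window of -1 day), not for whether the result must be in hand.

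Section 8.2.5, under Pregnancy Testing, asks for a highly sensitive serum test at screening and then for a second test: a "highly sensitive serum or urine pregnancy test should be completed within 7 days of initiation of investigational product". Testing continues around day 1 of each cycle. A Table 1-1 footnote treats the tests after screening as separate time points: "For all other time points, a highly sensitive serum or urine pregnancy test is required". Table 11-1 (Section 11.2) lists "Serum or urine pregnancy" among the local laboratory tests.

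The eligibility bar is criterion 216: "Female subjects with a positive pregnancy test assessed at screening by a highly sensitive serum pregnancy test". On the age of that screening test, Section 8.1.1 says: "All screening procedures must be performed within 28 days prior to start of investigational product administration, unless otherwise noted".

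**The concern.** A second pregnancy test near initiation can do one thing that later tests cannot: prevent the first exposure. It does so only if someone reads it before the drug is given. The waiver in Section 8.1.2 is sensible for routine safety laboratory tests in later cycles, where holding every dose for results would be impractical. Applied to the first dose, it removes the preventive value of a test that the protocol already requires.

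Section 11.5 requires counseling about fetal risk from pregnancy during treatment. Section 8.2.4.6 withholds further doses once a pregnancy is known, so it acts only after exposure has begun. The stake is subject safety. No endpoint, dose decision, analysis set or estimate changes.

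**Working it through.** The plan gives no figure on this point, so there is none to reproduce. The check is a comparison of provisions followed by window arithmetic.

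**Does the waiver reach the pregnancy test?**

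1. The rule in Section 8.1.2 covers any predose laboratory test.
2. Table 11-1 lists the pregnancy test as a local laboratory test.
3. Predose means any time before dosing, and laboratory work for cycle 1 day 1 may be drawn one day early. A sample taken on day -1, or on day 1 ahead of the dose, therefore qualifies.
4. It follows that the waiver covers a second pregnancy test drawn at either time.

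**Does another provision override it?**

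- Section 8.2.5 says the test should be completed. Section 8.2 and the Table 1-1 footnotes also require predose assessments to be completed before dosing, while Section 8.1.2 says results need not be available. In this protocol, completing a test and having its result are different things.
- Section 8.2.5 fixes the timing relative to initiation without the word *before*.
- Criterion 216 is tied to the screening serum test, not the later one.
- Section 8.1.1 makes the last pre-treatment result count when an eligibility laboratory test is repeated during screening. It does not name the second pregnancy test, which the Table 1-1 footnote treats as a separate time point and which may be a urine test.
- Criterion 214 excludes women "who are unwilling to use 1 highly effective method of contraception during treatment of AMG 510" and for 7 days afterwards. Its wording does not reach back to the interval between the screening test and the first dose.

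None of these expressly requires the second result to be read first.

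**Age of the latest known result at first dose**

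Let *s* be the age in days of the screening serum test at first dose (at most 28, Section 8.1.1) and *t* the age of the second sample. The latest known result has age *t* if the second test has been read and *s* if it has not.

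- Second sample on day 1 before dosing (*t* = 0): read, 0 days; unread, up to 28 days. Largest difference: 28 - 0 = 28 days.
- Second sample the day before (*t* = 1): read, 1 day; unread, up to 28 days. Largest difference: 28 - 1 = 27 days.
- Second sample at any time in the 7 days before initiation, and read: at most 7 days.

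These are upper limits. A subject screened closer to dosing has a smaller *s* and loses less. An unread result is realistic mainly for *t* = 0 or 1, because an earlier sample would normally be reported by the time of dosing.

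**Number affected.** At most 18 subjects (6 + 12) are planned, or at most 12 if only the 960 mg cohort is used. The number of females of childbearing potential is not given, nor is any rate of positive second tests, so no probability is calculated.

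**The case against.** The strongest reply is that other text already closes the gap. Section 8.2 runs the screening window to day 1, pregnancy status determines eligibility, and Section 8.1.1 says the last pre-treatment result of a repeated eligibility test must be considered, which is impossible if it is unread. A specific pregnancy-testing rule in Section 8.2.5 should also prevail over a general rule for the treatment period, and a test placed at initiation is naturally meant to be acted on. This has force as a statement of probable intent. It does not settle the wording: criterion 216 names the screening serum test, the footnote separates later time points, and Section 8.1.2 is an express permission.

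Several limiting points stand in full:

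- The pregnancy-test row of Table 1-1 is not shown and the laboratory manual is not available, so it cannot be confirmed that the schedule puts the second test on day -1 or day 1.
- Apart from abstinence, the accepted female methods in Section 11.5 (intrauterine device, tubal ligation or occlusion, vasectomized partner) are normally in place well before treatment. Criterion 217 also excludes women planning pregnancy on study. The contraceptive interval is therefore a gap in wording more than in practice.
- The documents quantify no embryo-fetal effect, and Section 2.2.2.3 reports no significant genotoxic risk.

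A reader might infer that eligibility laboratory results in general may go unread before the first dose. The documents do not support that: Sections 5.1, 5.3 and 8.1.1 require all criteria to be met, and a repeated result to be used, in the eligibility decision.

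**Conclusion.** The point holds in a narrow form. Section 8.1.2 permits the first dose to be given with the second pregnancy test unread, and Section 8.2.5 does not withdraw that permission. For a sample drawn on day -1 or on day 1 before dosing, the latest known result may be up to 28 days old when one 0 to 1 day old was obtainable.

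A reader might go further and conclude that the protocol has no pregnancy check before exposure, or that it lets women known to be pregnant be dosed. Neither follows. Criterion 216 excludes a positive screening serum test, and Section 8.2.4.6 stops dosing once pregnancy is known. What is lost is the recheck, not the gate. Nor do the documents show that an unread result would be common.

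The conclusion assumes that the pregnancy-test row of Table 1-1 and the laboratory manual contain no contrary instruction. Severity is low: a cheap improvement in subject safety that affects few subjects on one occasion each.

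**What to change.** Add one sentence to Section 8.1.2: *For the first dose only, in females of childbearing potential, a negative result from the pregnancy test done within 7 days before initiation must be reviewed before AMG 510 is given.* In Section 8.2.5, in the clause "highly sensitive serum or urine pregnancy test should be completed within 7 days of initiation of investigational product", replace *of* with *before* ahead of *initiation*. Keep the existing allowance for all later doses. No sentence on repeated eligibility tests is needed, because the current text covers them.

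The change adds no test and no visit. The test is run locally, urine is accepted after screening, and the -1 day window lets the sample be taken the day before. The downside is that an occasional first dose waits for a same-day result. Where sites already read the test first, the edit only records what they do.
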